Study 2 will evaluate the effects of extended exposure to VLNC cigarettes in smokers of childbearing age with < an Associate's Degree. This study will be limited to two conditions: usual brand versus the 0.03 mg dose. After a baseline period in which daily smoking rate and other baseline assessments are completed, participants will be randomly assigned to usual brand or the VLNC condition and followed for 12 weeks. Participants must have technological capabilities to complete weekly face-to-face video assessments and use a smartphone-compatible smokerlyzer for assessing breath carbon monoxide (CO) levels.

Study 2 Screening Procedures

Recruitment:

A sample size of 90 completers is proposed to test the primary aim in Study 2. Anticipating 15% attrition, and five pilot participants (3 at UVM, 2 at the University of Kentucky [UKY]), 111 participants will be enrolled across both sites (74 at UVM, 37 at UKY). Prior to study initiation and participant recruitment, IRB approval will be obtained from the University of Vermont's IRB and University of Kentucky's IRB. Potential participants will respond to community advertisements (local newspapers, community bulletin boards, Facebook, Craigslist, city buses, direct mailers etc.) that contain a study description, link to an

online survey and the name and phone number of the Research Assistant. Direct mailers are mass mailings that are sent to all addresses in a given zip code and are not sent to particular individuals. Mailers will include contact information for the research study so recipients can contact us if they are interested in participating. Potential participants will also be recruited from obstetric practices, WIC offices, and behavioral health programs in Vermont. Pregnant women at these locations will be asked to complete a brief self-administered smoking-screening form containing a multiple-choice question on smoking status that has been validated to enhance accurate reporting (Mullen et al., 1991). This form will be used specifically for research recruitment purposes. Pregnant women who endorse smoking currently will be given the option to sign the smoking-screening form and provide a phone number at which they can be contacted about the study. A study team member will physically collect signed smoking-screening forms to securely transfer them to study offices. Signed forms will be stored in a locked file cabinet in a locked office which participants do not have access to.

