Participants will receive a follow-up phone call between 25 and 35 days after the abstinence assessment session to assess their smoking patterns. The phone questionnaire will last less than five minutes. The questionnaire will ask if the participant is still smoking, how much and whether she has attempted to quit smoking since the end of the study. Participants will receive 5 variable incentive program lottery tickets for completing the call as compensation. Those who report abstinence will be invited to complete for biochemical verification and be compensated \$40 for doing so. A urine sample will be collected to test urine cotinine levels. Additionally, any Medical Event Forms that remain open from the last session will be discussed.

Once a participant has completed all study procedures and all open events have been closed, the PI or project manager will review the participant's records and sign a form indicating study completion for that participant.

Birth Outcomes Data

Researchers will collect birth outcome data through review of maternal birth medical records.

Study 2 Randomization

At the end of the Baseline 2 session, participants will be randomized into one of two cigarette conditions. Participants in each condition will be assigned cigarettes that match their menthol preference. Participants will be randomized, using block randomization, in equal number to the dose conditions, with randomization stratified by study site and menthol status. Each site will randomize participants until the total goal of 106 participants across both sites is reached, and no effort will be made to recruit a specific number of menthol and non-menthol smokers at each site.

Condition	TPMF Code	Type*	Specifications Nicotine Yield	Specifications Tar Yield	Specification Range for Nicotine Yield	Specifications Nicotine Content
2	NRC102	RN	0.03 ± 0.01	9 ± 1.5	0.02 - 0.04	0.37 ± 0.01
2	NRC103	RN-Men	0.03 ± 0.01	9 ± 1.5	0.02 - 0.04	0.39 ± 0.00
3	N/A	Usual Brand	N/A	N/A	N/A	N/A
3	N/A	Usual Brand-Men	N/A	N/A	N/A	N/A

*Legend:	
RN	Reduced Nicotine
RN-Men	Reduced Nicotine-Menthol

The lead statistician will create a randomization schedule for each of the two sites, amounting to 150% of expected enrollment at each site. The excess randomization codes will be used in the event that a site will have to enroll extra participants due to unexpectedly slow enrollment at another site.

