The Primary Aim of Study 2 is to compare the effects of cigarettes varying in nicotine yield on smoking rate. The primary endpoint is cigarettes per day (CPD) at 12 weeks. CPD will be collected by daily IVR and/or TLFB at each session to assess cigarette use in the days since the last interview. This will yield a continuous record of cigarette use throughout the study. A weekly average will be obtained for analysis by averaging CPD from the previous visit to the current visit. Additional measures addressing this aim are breath CO level, urinary cotinine concentration, and nicotine dependence (FTND, WISDM) scores. Secondary Aim 1 is to assess adherence to assigned tobacco products and use of multiple nicotine

products during extended exposure. Secondary Aim 2 is to quantify the effects of VLNC cigarettes on (a) biomarkers of exposure to tobacco carcinogens (urine total cotinine, NNAL, PAH)s.

To examine these Aims, repeated measures analysis of variance (ANOVA) will be used for outcomes that are measured repeatedly from baseline to the end of the treatment phase. Each repeated measures ANOVA model consists of five terms: cigarette condition effect, visit effect, interaction effect between cigarette condition and visit, random subject effect (between-subject error), and random error (within-subject error). The variance-covariance structure will be specified as the first-order autoregressive, and variance parameters will be estimated using restricted maximum likelihood method with the Satterthwaite approximation. First, the VLNC condition will be compared to the usual brand condition; if significant differences are observed ($p < 0.05$), the simple effects of visit will be examined within the VLNC condition and the usual brand condition. Biomarkers will be analyzed on natural log scales so that ANOVA model assumptions of normality and equal variances hold. Geometric means in original units will be calculated as well. Interaction terms between BMI and cigarette condition will be added to these models to explore possible moderating effects of obesity on the relationship between cigarette condition and biomarkers. Differences between groups in self-reported quit and cigarette reduction rates at the 4-week post-treatment follow-up period will be evaluated using Chi-square tests, as will be the case for other discrete outcomes such as drop-out rates. SAS (SAS Institute Inc., USA) will be used for most analyses, but may be supplemented by use of STATA or R.

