### 6.2. Secondary Endpoints

- Measures of depression and anxiety
  - Collected at the second baseline and Weeks 1, 2, 3, 4, 5, 6, 7, 8, 9, 10, 11 and 12

- Beck Depression Inventory
  - Overall Anxiety Severity and Impairment Scale
- Adherence to assigned tobacco products
  - Collected through the daily IVR system
- Use of multiple nicotine products.
  - Collected through the daily IVR system
- Biomarkers of exposure to tobacco carcinogens
  - Collected at the second baseline and Weeks 6 and 12
- Study retention
- Quit attempts and spontaneous quitting
  - Assessed at weekly visits and at the 30-day post-intervention assessment

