#### **7.4. Secondary Endpoint Analysis**

Repeated measures analysis of variance will be used for the analysis of most secondary endpoints. Analyses will conform to the methods outlined above for primary endpoints. These outcomes include use of other nicotine products and biomarkers of exposure to tobacco carcinogens. Use of multiple nicotine products will be collected through the IVR system, as the response to questions asking whether the participant used smokeless tobacco, e-cigarettes or nicotine replacement products. Because responses are recorded as Yes/No, the responses will be aggregated on a weekly basis and are expressed as the number of days that other nicotine products are used.

Biomarkers will be analyzed on natural log scales so that ANOVA model

assumptions of normality and equal variances hold. Geometric means in original units will be calculated as well. Interaction terms between BMI and cigarette condition will be added to these models to explore possible moderating effects of obesity on the relationship between RNC cigarettes and biomarkers.

Differences between groups in self-reported quit and cigarette reduction rates at the 30 day post-intervention follow-up period will be evaluated using Chi-squared tests, as will be the case for other discrete outcomes such as drop-out rates. Secondary analyses using logistic regression will be completed to identify factors associated with cessation and retention. Candidate factors, in addition to condition, include subjective responses to the products, willingness to pay for the product (CPT), and withdrawal. SAS (SAS Institute Inc., USA) will be used for all analyses.

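### Study 2 compares 30-day quit rates on self-report alone, although women know their arm and the protocol already collects urine cotinine from those who report abstinence

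*SAP*

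**What the plan says.** - **Analysis.** SAP Section 7.4 plans chi-squared tests, at the 30-day follow-up, of "Differences between groups in self-reported quit and cigarette reduction rates". The protocol (Study 2 Statistical Methods and Sample Size) agrees: "Differences between groups in self-reported quit and cigarette reduction rates at the 4-week post-treatment follow-up period will be evaluated using Chi-square tests".
- **Endpoint.** SAP Section 6.2 lists quit attempts and spontaneous quitting as a secondary endpoint: "Assessed at weekly visits and at the 30-day post-intervention assessment". It does not define a quit.
- **Data collection.** The protocol (30 Day Follow up Phone Call) describes a call of under five minutes, 25 to 35 days after the abstinence session. "The questionnaire will ask if the participant is still smoking", how much, and whether she has tried to quit.
- **Verification.** The same section adds: "Those who report abstinence will be invited to complete for biochemical verification". Completing this pays $40. "A urine sample will be collected to test urine cotinine levels".
- **Conditions.** Protocol, Study 2: "This study will be limited to two conditions: usual brand versus the 0.03 mg dose". Sites buy the usual brand cigarettes.

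Neither document says how the cotinine result enters the quit analysis. Neither gives a cut-off for abstinence at this call, a rule for women who decline or fail verification, or a rule for a missed call. SAP Section 7.6 describes likelihood estimation and imputation. It does not say how an unverified quit is classed or which women form the denominator of a single binary comparison.

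**The concern.** The outcome is a short telephone answer from a woman who knows which product she was given. The label open-label does not appear in the documents. It follows from the design: one arm receives a familiar commercial brand and the other a research cigarette, and the blinding text sits in the Study 1 sections. The blinded safety review by investigators, in the protocol's DSMB section, does not mask a woman who reports her own smoking.

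Elsewhere the protocol does not take self-reported tobacco use at face value. Staff assess truthfulness at each screening and baseline visit, the incentive programme includes a bogus pipeline, and the abstinence session requires a fall in breath CO. The 30-day quit comparison has a check available and leaves it out.

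A claim that very low nicotine cigarettes raise cessation in pregnant women would matter to the regulator. If women in one arm over-reported quitting more than those in the other, the planned analysis could not separate that from real quitting. SAP Section 7.4 also plans logistic regression for factors associated with cessation, so an unclear definition would carry over into that model.

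**Working it through.** **1. Inputs from the documents.** There are 90 completers, 45 per arm. With 15% attrition, 90/(1 − 0.15) = 105.9, so 106 are randomised, or 53 per arm. Adding 5 pilots gives 111, which matches the stated enrolment. The documents give no quit rate, false-report rate or power for the quit endpoint, so there is no figure of the plan's own to reproduce.

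**2. Assumed inputs.** Let q be the true quit rate, equal in both arms, and f the share of continuing smokers who falsely report quitting. The reported rate is q + (1 − q)f. With q = 0.10:
- f = 0.10 in one arm: 0.10 + 0.90 × 0.10 = 0.190
- f = 0.03 in the other: 0.10 + 0.90 × 0.03 = 0.127

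**3. Rejection probability.** For a and b reported quitters of n per arm and p = (a + b)/(2n), the uncorrected statistic is X² = [(a − b)/n]² / [p(1 − p) × 2/n]. Summing the product of the two binomial probabilities over all (a, b) with X² above the 5% critical value gives the exact rejection probability. For 19.0% v 12.7% and n = 53 it is 14.0%; for n = 45 it is 13.6%.

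**4. Range if only one arm over-reports (f = 0 in the other).**

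| True rate | n per arm | f = 0 | f = 5% | f = 10% | f = 20% |
|---|---|---|---|---|---|
| 5% | 45 | 4.9% | 15.3% | 36.2% | 78.2% |
| 5% | 53 | 4.4% | 14.3% | 38.1% | 83.0% |
| 10% | 45 | 5.9% | 10.8% | 23.9% | 61.6% |
| 10% | 53 | 4.9% | 10.5% | 25.5% | 67.6% |
| 25% | 45 | 5.4% | 7.3% | 12.9% | 34.1% |
| 25% | 53 | 5.3% | 7.5% | 14.1% | 38.7% |

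If verification removed every false claim, rejection would return to the f = 0 column.

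**5. Is the chi-squared test itself at fault?** Expected quit counts fall below 5 per arm when the pooled rate is under 5/45 = 11.1% or 5/53 = 9.4%, so sparse cells are possible. With equal true rates from 1% to 50%, the exact size of the uncorrected test is at most 5.3% at n = 53 and 6.0% at n = 45. At n = 53 and a 3% quit rate it is 3.0%. Fisher's exact test at n = 53 has size 0.2% at a 3% quit rate, 0.8% at 5%, 1.9% at 10% and 3.0% at 25%.

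**The case against.** **No evidence of differential reporting.** The false-claim rates above are assumptions. By the 30-day call both arms have been told to stop study product, and both hear the same closing script. A reader might infer that the planned comparison will show a spurious VLNC effect. The documents do not support that: knowing one's arm makes differential reporting possible but does not show it. Even the 10% v 3% example rejects in only about 14% of trials. This stands, so the point is about exposure to bias, not a demonstrated bias.

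**The test.** A reader might also infer that chi-squared is too liberal with few quitters and should give way to Fisher's test. Pairs such as 8/53 v 2/53 (p = 0.046 v 0.093) or 6/53 v 1/53 (0.051 v 0.113) seem to say so. The exact sizes show that these gaps reflect Fisher's conservatism. Changing the test would cost power and correct almost nothing.

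**Cotinine is an imperfect check.** Nicotine replacement and e-cigarettes raise it, and the closing script leaves room for medication use. Leftover VLNC cigarettes may not raise it much, although remaining unused product is to be collected. Verification is by invitation and only for women who report abstinence, so uptake could itself differ by arm. All of this stands. It shapes the fix without making self-report alone preferable.

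**Scope.** The endpoint is secondary, and protocol and SAP agree and openly call it self-reported. There is no contradiction between the documents. The reduction rate in the same sentence has no verification step and is outside this point.

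**Conclusion.** The gap is real and narrow. The quit comparison rests on unverified answers from unmasked women, while a cotinine result that the protocol already provides for is left without a use, a cut-off or a missing-data rule. The size of any bias cannot be derived from the documents. Under the assumed inputs, the chance of a false difference is about 14% for false claims of 10% v 3% with 10% true quitting. Across the one-arm scenarios with f of 5% to 20%, it runs from about 7% to 83%. If over-reporting is equal in the two arms and true quitting is equal, no false difference is created. These figures assume that every woman's 30-day answer is obtained. The chi-squared test is adequate at 45 to 53 per arm. The primary endpoint, Week 12 CPD, is not affected. This is a cheap improvement, not a flaw that undermines the trial.

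**What to change.** In SAP Section 7.4:
1. Make cotinine-verified abstinence at the 30-day follow-up the main quit analysis. State the cut-off and the window for the urine sample before the data are examined.
2. Use the full analysis population of Section 5.1 as the denominator. Count women who decline or fail verification, or who miss the call, as not abstinent.
3. Keep self-reported quitting as a sensitivity analysis, and report call completion and verification uptake by arm.
4. Add a sensitivity analysis for women who report nicotine replacement or e-cigarette use. The protocol's outline of the call does not mention these products, and the SAP collects them by IVR. A question at the call is needed unless the form already has one.
5. Apply the same definition of cessation in the planned logistic regression.
6. Keep the chi-squared test, and leave the reduction rate self-reported and labelled as such.

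The cost is SAP wording, a cut-off to agree, and possibly one extra question; the urine collection is already in the protocol. The downside is that some true quitters who give no urine, or who use other nicotine products, count as not abstinent. A low cotinine value also cannot exclude continued use of leftover VLNC cigarettes. If verification uptake differs by arm, the verified result must be read beside the self-reported one.

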#### **4.2. Sample Size**

Sample size was determined using power analysis for hypothesis tests related to the Primary Aim of Study 2, specifically to detect a significant difference between the VLNC condition and the UB condition in the primary endpoint, cigarettes per day (CPD), at the end of the trial. Effect size estimates were based on our previous studies of normal nicotine cigarettes (NNC) and VLNC use in disadvantaged women of childbearing age and estimates of CPD in our completed study on smoking topography in pregnant women and women of childbearing age. In that study, pregnant women smoked an average of 12.1 CPD, while preliminary data from our trial of women of childbearing age suggest a decrease of 5 CPD in women smoking VLNC compared to those smoking NNC. A sample size of 45 completers per condition will provide 80% power to detect statistically significant differences in smoking rate, with significance level alpha = 0.05.

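### The 30-day cigarette reduction outcome is an undefined yes/no rate tested by chi-squared, although the call already asks how much each woman smokes

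*SAP*

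**What the plan says.** SAP 7.4 (Secondary Endpoint Analysis): "Differences between groups in self-reported quit and cigarette reduction rates at the 30 day post-intervention follow-up period will be evaluated using Chi-squared tests". It puts these rates with discrete outcomes: they "will be evaluated using Chi-squared tests, as will be the case for other discrete outcomes such as drop-out rates". The protocol, under Study 2 Statistical Methods and Sample Size, plans the same: "Differences between groups in self-reported quit and cigarette reduction rates at the 4-week post-treatment follow-up period will be evaluated using Chi-square tests". SAP 13 proposes no changes to the protocol's analyses, so the protocol's undefined term carries over.

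Neither document defines a reduction. SAP 6.2 does not fill the gap: quit attempts and spontaneous quitting are "Assessed at weekly visits and at the 30-day post-intervention assessment", but reduction is not in its list, nor in the protocol's Outcome Variables.

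Under 30 Day Follow up Phone Call, the protocol says of the questionnaire that it "will ask if the participant is still smoking, how much and whether she has attempted to quit smoking". SAP 7.3.1 models CPD as a continuous outcome, at baseline and Week 12 and then over 13 time points, and stops at Week 12.

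**The concern.** There are two separate problems.

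**Meaning.** With no minimum change and no reference point, the analyst has to choose the rule, possibly after seeing the data. Under a loose rule, ordinary variation puts many unchanged women among the reducers in both conditions, and the reported percentages would be hard to read.

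**Efficiency.** Splitting a count into yes/no discards how far each woman moved. The amount is asked on the call and baseline CPD is already held, so a sharper comparison needs no new data. This is the only between-condition comparison of post-treatment reduction that the plan specifies.

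**Working it through.** **Inputs.** SAP 4.2 gives 45 completers per condition, 80% power, a 5 CPD difference, a mean of 12.1 CPD in pregnant women, and the test "with significance level alpha = 0.05" (two-sided assumed). No SD is given, and no power is stated for the 30-day outcome.

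**1. The plan's own figures.** Enrolment reproduces: 90/(1 − 0.15) = 105.9, so 106, plus 5 pilots = 111. The 80% power cannot be checked without an SD, so I solved for it:

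SD = 5 × √(45/2) / (1.960 + 0.842) = 8.47 CPD (8.37 using the t distribution), so d = 5/8.47 = 0.59.

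This SD belongs to Week 12 CPD. Using it, and the 5 CPD effect, at 30 days is an assumption.

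**2. Power with normal change scores.** Assume equal SDs, no mean change on usual brand, and any decrease counted as a reduction.

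- Reducers: usual brand Φ(0) = 0.500; VLNC Φ(0.5906) = 0.7226; average 0.6113.
- Chi-squared: [0.2226 × √45 − 1.960 × √(2 × 0.6113 × 0.3887)] / √(0.2500 + 0.2005) = (1.493 − 1.351)/0.671 = 0.21, so power is Φ(0.21) = 58%.
- Amount smoked: 0.5906 × √(45/2) − 1.960 = 0.84, so power is 80% (by construction).
- Chi-squared needs 75 per condition for 80% power, against the 45 planned: 75/45 = 1.67 times as many.

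| d (45 per condition) | Any-decrease chi-squared | Amount smoked |
|---|---|---|
| 0.3 | 20% | 30% |
| 0.4 | 32% | 47% |
| 0.5 | 46% | 66% |
| 0.59 | 58% | 80% |
| 0.8 | 83% | 97% |

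At d = 0.59 the figures are 51% and 73% with 38 per condition, and 66% and 86% with 53.

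**3. Does a minimum change recover the power?** Not in this model. Required falls of 1, 2, 5 and 6.05 CPD (half of 12.1) give 59%, 60%, 58% and 57%. A threshold repairs the meaning; here the loss comes from dichotomising.

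**4. Unchanged women called reducers** (simulated, true smoking constant):

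- Any decrease, answer compared with a non-integer baseline weekly mean: 50–52%.
- Any decrease, both values whole numbers: 26–45%, because ties do not count.
- Any decrease, both values rounded to 5 or 10: 3–29%.
- A fall of at least 6.05 CPD in the model of step 2: Φ(−6.05/8.47) = 24%. A 50% cut with skewed CPD: 12–18%.

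**5. Skewed CPD.** Simulations used 45 per condition, gamma-shaped CPD with mean 12.1 and SD 8.37, and baseline-to-follow-up correlation 0.5–0.7.

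- 5 CPD as a proportional effect: any-decrease chi-squared 74–92%, baseline-adjusted CPD 98–99.9%, a 50% cut 72–87%.
- 2.5 CPD, proportional: 19–32% against 41–56%.
- 5 CPD as a constant shift floored at zero: 77–91% against 86–95%.
- 5 CPD across proportional, constant-shift and quit-driven effects: 54–91% against 84–99.8%. As 84% is the lowest adjusted figure, the gap where chi-squared has 54% is at least 30 points.
- Under the constant-shift and quit-driven effects, a 50% cut reached 95–99%, against 84–95% for adjusted CPD.

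The proportional figures flatter both methods. Scaling shrinks the VLNC SD to 8.37 × 7.1/12.1 = 4.9, so an unadjusted t-test has about 94% power instead of 80%. With the SD held at 8.37, adjusted CPD gives 90% at correlation 0.5 and 97.5% at 0.7.

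**The case against.** The sponsor could fairly say that reduction is not a listed endpoint, that the primary CPD comparison is already continuous, and that a clearer definition is all that is needed. It could add that the SD and the 5 CPD effect come from end-of-trial planning, whereas participants are told to stop the research cigarettes at Week 12; nothing in the documents supports either figure 30 days later. The response format of the call is not shown, so the amount may not be a CPD count. All of this stands. It limits how precisely the loss can be sized and keeps the point secondary. It does not supply a definition, or a between-condition analysis of the amount.

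Stronger readings are tempting but not supported:

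- *Any drop below baseline counts, so half of unchanged women are reducers.* The documents state no rule at all. The half holds only under that assumed rule with few ties.
- *The test is invalid.* Chance reducers arise in both conditions, so the between-condition comparison keeps its error rate.
- *It is the only post-treatment smoking comparison.* The same sentence compares quit rates, and the Gestational Week 28 call collects seven-day use from women who finish the study before then.
- *The amount is thrown away.* The protocol says continuous outcomes will be summarised descriptively. What is missing is a between-condition analysis at 30 days.
- *A 50% cut-off never helps.* Step 5 shows that it can beat adjusted CPD under a constant-shift or quit-driven effect.

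**Conclusion.** The point holds as a secondary-outcome weakness that is worth correcting. The 30-day reduction outcome is dichotomised and undefined, and a more informative comparison is available from data the plan already intends to collect.

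Adjusted CPD beat the any-decrease test in every setting examined. The size of the gain is illustrative: 22 points (58% against 80%) with normal change scores at d = 0.59, and from about 4 points to more than 30 with skewed CPD. It rests on an any-decrease rule that the documents do not state, an SD implied by the Week 12 power statement, and an effect assumed to persist after the product is stopped. The primary endpoint is not affected.

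**What to change.** In SAP 7.4 and in the protocol's Study 2 Statistical Methods:

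1. Make CPD reported on the 30-day call, set to zero if not smoking, the main reduction comparison, using a linear model for condition adjusted for baseline CPD. Confirm that the call form records cigarettes per day.
2. Keep chi-squared for quit and drop-out rates.
3. If a reduction rate is kept, report it as supplementary, with a pre-specified reference point (baseline CPD), a minimum change such as 50%, and a rule for quitters and for women not reached.

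The cost is a change of wording, with no new data provided the form records a daily count. The headline becomes a mean difference instead of a percentage of women. A 50% responder rate can be more sensitive when the effect comes mainly from quitting, but the retained quit-rate test covers that case.
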